1.0 BACKGROUND AND RATIONALE

1.1 Study Synopsis

In this proof-of-concept study, our multidisciplinary team will conduct a pilot randomized clinical trial to test the feasibility of the innovative *Patient-Reported Outcomes-Informed Symptom Management System* (PRISMS) to enhance personalized supportive care for cancer patients and caregivers during post-treatment care transition. PRISMS was formerly known as PROCESS (Patient-Reported Outcome-Informed Caregiving Education and System Management System). We will randomly assign 20 colorectal and bladder cancer (CBC) patients who transition from post-ostomy creation hospital care to self-management at home and their caregivers to either the PRISMS or usual care groups (a total of 40 individuals). We will conduct pre- and post-assessments of QOL and PRO (symptoms) at baseline upon enrollment and 3 months later. If results indicate that PRISMS is feasible and beneficial, we will design and conduct a definitive trial to examine the efficacy of PRISMS, a potentially scalable intervention that can be disseminated through oncology clinics nationwide to enhance post-treatment care for CBC patients with ostomies and their caregivers.

1.2 Background

The third and fourth most common cancers in the US respectively,¹ colorectal and bladder cancer (CBC) affects more than 100,000 patients each year.² CBC disproportionately affects older patients, with median age of diagnosis 63 years and 75 years for colorectal and bladder cancer, respectively.¹ After ostomy surgery, a major treatment option,¹ patients often encounter significant symptoms and complications (e.g., dehydration, infection) and wound care problems.^{3,4} These symptoms and complications are associated with reduced quality of life (QOL)⁵⁻⁷ and high rates of morbidity and mortality.^{8,9} Poor symptom management is also a primary reason for emergency room visits,¹⁰⁻¹² hospital readmission,^{4,9,13} and high costs of care for patients with ostomies.⁴ There has been limited research to support cancer patients and caregivers to manage symptoms, improve QOL, and reduce preventable hospital visits and their related costs while CBC patients transition from in-patient care to post-treatment self-care at home.

To address these issues, our team has developed a web-based mHealth symptom and complication monitoring and self-management program for CBC patients with ostomies and their family caregivers, known as PRISMS. PRISMS is a personalized/customized mHealth program that integrates patient reported-outcomes (PRO) measures and technology in enhancing program relevance and usefulness, and improving human-technology interaction and information delivery, all of which predict use of technology-delivered programs.

PRISMS aims to provide monitoring, education, skills training, and social support to ameliorate the complex, interrelated symptoms and complications, and ultimately, improve QOL. PRISMS includes modules addressing ostomy care, the *most common* complications (e.g., dehydration, skill problems) and related

physical and psychosocial symptoms (e.g., fatigue, sleep disturbance, emotional distress, and sexual dysfunction), and safe physical activity for speedy recovery (while preventing hernia and falls). PRISMS integrates PRO (e.g., fatigue) and objective data from wearable devices (smart bottle and smart scale that monitor fluid intake and loss) to provide continuous monitoring of patients' symptoms and complications after they are discharged home. PRISMS triages patient care based on the monitoring data that indicate severity of their symptoms and complications. Patients and caregivers will self-monitor and manage at home for mild and moderate symptoms but be referred to professionals (e.g., wound and stoma nurse) when the patient experiences severe symptoms or significantly worsened symptoms. PRISMS also provides moderated online forum to promote peer support among study participants who face similar challenges, as well as "Let's Chat" to facilitate professional support.

1.3 Purpose and Rationale

This is a pilot randomized clinical trial (RCT) using mixed methods. We will examine the feasibility of PRISMS by conducting a two-armed pre-post pilot RCT study and interviews to obtain feedback from participants who use PRISMS. Study participants - twenty CBC patients with new ostomies and their caregivers (N=20 dyads, i.e., 40 individuals) - will be randomly assigned to either the PRISMS or usual care groups.

2.0 STUDY OBJECTIVES AND ENDPOINTS

The objective of this pilot randomized clinical trial is to test the feasibility of the innovative PRISMS program to enhance personalized supportive care for cancer patients and caregivers during care transition. The aims that will help gather preliminary data for a larger definitive trial are listed below. The indicators of feasibility will include recruitment, enrollment and retention rates as well as automatic recorded online activity comprising navigation time, number of logins, utilization of program sections, which we will collect the data using administration log and study website.

The study outcome, Quality of life (QOL), will be assessed at T1 and T2 using the 27-item Functional Assessment of Chronic Illness Therapy general scale (FACT-G).⁹⁴ We will measure general QOL and physical, social/family, emotional, and functional subdomains.⁹⁵ Caregivers will report QOL using the spouse's version of FACT-G with slightly modified wording.⁹⁶ We will use the PROMIS measures of fatigue, pain, sleep disturbance⁹⁷⁻¹⁰⁰ and Cancer Anxiety¹⁰¹ and Depression¹⁰² to assess patient and caregiver symptom distress at T1 and T2. We will also collect participants' demographics (age, race/ethnicity, income, education) and patient treatment information at T1. At T2, we will collect quantitative data on participant satisfaction of and comfort with using PRISMS.

2.1 Primary Objective

To examine the feasibility of delivering PRISMS to patients and caregivers (as assessed by the recruitment, enrollment, and retention rates, and satisfaction

with and perceived ease of use of PRISMS).

2.2 Secondary Objectives

To estimate the magnitude of benefit of PRISMS. We hypothesize that, compared with the patients receiving usual care, the PRISMS users will report (1) greater improvement in their primary outcomes of QOL (overall, physical, emotional, and social QOL); and (2) fewer post-treatment care services related to stoma complications (e.g., ER visits, readmission, use of healthcare providers) from between T1 and T2.

3.0 PATIENT ELIGIBILITY

3.1 Inclusion Criteria

Patients must (1) have been surgically treated for bladder or colorectal cancer; (2) have a newly created ostomy within the past 4 weeks, and (3) have a caregiver who is willing to participate in the study. The caregiver must (1) be 18 years and older, (2) be identified as the primary caregiver by the patient. We will also recruit 3-5 providers who provide direct post-surgical care to CBC patients to provide feedback on the PRISMS. Providers, patients and caregivers will be recruited from the LCCC urologic (GU) and *gastrointestinal (GI)* oncology in- and out-patient units.

3.2 Exclusion Criteria

Patients and their caregivers will be excluded if they are unable to read, speak, or understand English. Have other cancer excluding non-melanomatous skin cancer or have cognitive impairment.

4.0 STUDY PLAN

4.1 Schema

We will recruit patients and caregiver dyads based on procedures used successfully in the past.^{83,93} After PRC and Institutional Review Board (IRB) approval, we will inform the health care providers working at the GU and GI units and obtain their permission to display the flyers of our PRISMS study (with our contact information) on the information board at the units.

A research team member will meet the patients who express interest in the PRISMS study by calling the research office or informing the professionals on the UNC LCCC in-patient GU or GI unit prior to their discharge home. The research team will provide study information, answer questions, screen the patient and caregiver for eligibility and willingness to participate, obtain informed consent, and collect baseline (T1) data (demographics, QOL, and symptom distress). The coordinator will then schedule a home visit to install PRISMS within 48 hours of discharge and train participants to use the study devices. Patients and caregivers

will use the PRISMS for 3 months—the period of time that patients have the highest risk for complications and related ER visits and readmission. Participants will be instructed to synchronize their devices daily. Participants will be contacted via telephone and email after 3 months to conduct the follow-up interview (T2) and collect the devices.

4.2 Duration of Study

The study will be conducted for 3 months among CBC patients and caregivers. There will be a survey at the beginning and end of the 3 months. The providers will be in the study one time for about 30-45 minutes to complete an interview.

4.3 Study Details

The coordinator will meet the patients who express interest in the PRISMS study by calling the research office or informing the professionals the GU or GI units prior to their discharge home. (Note: However, the clinician Co-Is and the PI will meet in early September to explore the possibility and procedure of enrolling potential participants prior to surgery. Once we have the details we will modify the study protocol immediately.) The coordinator will provide study information, answer questions, screen the patient and caregiver for eligibility and willingness to participate, obtain informed consent, and collect baseline (T1) data (demographics, QOL, and symptom distress). The coordinator will then schedule a home visit to install the PRISMS within 48 hours of discharge and train participants to use the study devices. Patients and caregivers will use the PRISMS for 3 months—the period of time that patients have the highest risk for complications and related ER visits and readmission. Participants will be instructed to synchronize their devices daily. Participants will be contacted via telephone and email after 3 months to conduct the follow-up interview (T2) and collect the devices.

Our project coordinator will identify potentially eligible patients and caregivers and introduce to them the PRISMS study and answer any questions they may have via in-person meeting (before discharge) and via telephone (after discharge). Potentially eligible patients and caregivers will be provided study brochures and introductions, written or telephone informed consent (whichever is the most convenient for participants) will be obtained from all patients and their caregivers prior to any research activities. After informed consent, patients and caregivers will complete their baseline assessment of quality of life and symptom distress. The project coordinator will then schedule for a home visit to install the study devices within 48 hours after patient discharge. The coordinator will teach participants how to use the devices and synchronize data daily. Patients and caregivers will then be encouraged to use PRISMS as scheduled. The standardized schedule is twice a day for 3 days, then daily for two weeks, and finally weekly for the rest of the study. But the assessment schedule can be reset if new symptoms and complications appear or existing symptoms and complications worsen. That is, if the patient experiences severe symptoms, participants will be automatically directed to use PRISMS more often. The synchronization between the iPAD and wearable devices (Fitbit, smart scale, and smart bottle) is designed to be a 1-click process to ease PRISMS use for elderly participants because colorectal and bladder cancer disproportionately influence older people.

The follow-up assessment will be conducted via telephone approximately 3 months after baseline. Following T2 data collection, all patients and caregivers will be interviewed to obtain qualitative evaluation of their experiences using PRISMS and suggestions for improving PRISMS and the study design.

4.4 Expected Risks

There is minimal risk to participants. Compared to patients receiving routine post-surgical care at home, PRISMS will enhance symptom monitoring and personalized management. We will integrate the PRO measures and data from wearables into PRISMS to enhance routine symptom monitoring. If patient's symptoms and health conditions become severe or worsened, professional providers (e.g., the surgical oncology nurse navigator, residents) will be informed via email, which will prompt necessary medical intervention and professional follow-ups. Patients and caregivers will also be reminded to contact patients' providers directly if needed and to call 911 for emergencies. The research team is comprised of urologic and surgical oncologic surgeons and a medical oncologist. The team will meet monthly (or as needed) to review any potential adverse events and provide professional guidance on how to handle potential risks.

While the risk of this study is minimal, patients and caregivers will be informed that they can withdraw from the study at any time. All data collected will be saved on password-protected, encrypted shared drives on UNC campus. Qualitative data will be directly transcribed and coded; whereas quantitative data will be collected and stored using the NC TraCS-managed Redcap. Each participant will receive a unique identifier that will be used to store the de-identified quantitative and qualitative data, and to maintain participant anonymity. Data will be stored separately from patient identifying information on the secure UNC network servers. All data will be available only to study personnel with password protection.

4.5 Removal of Patients from Protocol

Participants can withdraw from study at any time.

5.0 TIME AND EVENTS TABLE

5.1 Time and Events Table

This study will recruit participants over a 2-month period (or until we successfully recruit 20 patient-caregiver dyads and 3-5 clinicians). Patient and Caregiver will be interviewed at the beginning and again at the end of 3 months. Each interview will last 30-45 minutes.

	Aim 1		Aim 2		
	Feasibility	Baseline	PRISM S (3-	Follow-up	Post-pilot exit interview
Recruitment	x				

Screening	x				
Informed Consent	x				x
Interviews	x				x
QOL ¹		x		x	
PRO symptoms		x		x	

6.0 UNANTICIPATED PROBLEMS

6.1 Definition

This study involves minimal risk to the participants.

As defined by UNC's IRB, unanticipated problems involving risks to study subjects refers to any incident, experience, or outcome that:

- Is unexpected (in terms of nature, severity, or frequency) given (a) the research procedures that are described in the protocol-related documents, such as the IRB-approved research protocol and informed consent document; and (b) the characteristics of the subject population being studied;
- Is related or possibly related to a subject's participation in the research; and
- Suggests that the research places subjects or others at a greater risk of harm (including physical, psychological, economic, or social harm) related to the research than was previously known or recognized.

6.2 Reporting

Any UPIRSO that occurs during the conduct of this study and that meets all three criteria listed in 6.1 must be reported to the UNC IRB using the IRB's web-based reporting system.

7.0 STATISTICAL CONSIDERATIONS

7.1 Study Design

This is a pilot randomized clinical trial (RCT) using mixed methods. We will conduct a two-armed pre-post pilot RCT study and interviews to obtain feedback from participants who use PRISMS. Study participants - twenty CBC patients with new ostomies and their caregivers (N=20 dyads, i.e., 40 individuals) - will be randomly assigned to either the PRISMS or usual care groups.

7.2 Sample Size and Accrual

We plan to recruit 20 patients with recent ostomy (within 4 weeks) and their caregiver (with a total of 20 patient-caregiver dyads and 40 individuals) and 3-5 health care providers. Based on previous experiences, we anticipate we will achieve data saturation among these participants. We claim such a study as

feasible if and only if both (i) recruitment rate (p) and (ii) retention rate (q) are large enough. More specifically, this is to test the following hypothesis: $H_0: p \leq 65\%$ or $q \leq 65\%$ vs $H_1: p \geq 80\%$ and $q \geq 80\%$. We will claim the study feasible (high recruitment rate and high retention rate) if we reach 29 or fewer patients/dyads to recruit 20 dyads, AND more than 14 (≥ 15 out of 20) participants remained in the study. This study reaches 76% power at alpha level 0.10. In addition, we will estimate the proportion and associated 95% confidence interval of patients' satisfaction with and perceived ease use of PRISMS. With 10 couples in the PRISMS arm and expected satisfaction rate of 70%, the width of the 95% CI will be around 0.58 (0.29 for 1-side width).

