7.3 Data Analysis Plans

The feasibility of successful delivery of PRISMS will be measured using indicators such as recruitment and retention rates. Analysis of these primary indicators are described above.

Appropriate descriptive statistics will be calculated for other indicators of feasibility, quality of life; general, and physical, social/family, emotional, and functional subdomains, for participants and partners, by time point (T1, T2), and by group, and patient's health care services utilization (e.g., clinic visits, ER visits, and readmission) by group. This sample size (10 in each group) will ensure 80% power to detect a large effect size of 1.15 at the one-sided 0.05 significance level using a two-sample t-test to compare the difference in pre-post change (from T1 to T2), or mean level at T2 (if an outcome is only measured at T2), of a given outcome between the two intervention groups.

Appropriate exploratory analyses (e.g., trajectory analysis of frequently measured PRO outcomes), for the purpose of generating hypotheses, may be conducted.

All analyses will be conducted using an intention-to-treat approach, in which all randomized participants will be analyzed according to their assigned group, regardless of the extent of intervention actually received. Due to the fact that this is an exploratory proof-of-concept study, rather than a confirmatory study, we will not adjust for multiplicity when computing the CIs in conducting comparisons. Unless otherwise specified, all tests will be one-sided at an alpha level 0.05. All analyses will be conducted using SAS 9.4 (SAS Institute Inc., Cary, NC).

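### The feasibility rule's alpha of 0.10 holds only when both rates are at or below 65%; under the stated "or" null the error reaches 0.33 or 0.23 with the other rate at 80%, and up to 0.41

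*Combined protocol and SAP*

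**What the plan says.** Section 7.2 (Sample Size and Accrual) calls the study "feasible if and only if both (i) recruitment rate (p) and (ii) retention rate (q) are large enough". The null hypothesis is p ≤ 65% or q ≤ 65%, where p is the recruitment rate and q the retention rate. The alternative is p ≥ 80% and q ≥ 80%.

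The decision rule has two limbs, and both must be met:

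- Recruitment: feasibility is claimed "if we reach 29 or fewer patients/dyads to recruit 20 dyads".
- Retention: "more than 14 (≥ 15 out of 20) participants remained in the study".

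The operating characteristics are given in one sentence: "This study reaches 76% power at alpha level 0.10". The section does not say at which values of p and q the 0.10 applies, and it does not mention independence of the two limbs. Section 7.3 (Data Analysis Plans) adds nothing on this test; it only refers back: "Analysis of these primary indicators are described above". The one-sided 0.05 default in Section 7.3 does not conflict, because it gives way where another level is specified, as Section 7.2 does.

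**The concern.** A null joined by "or" is true as soon as one rate is inadequate. Alpha for such a null is the largest probability of a false claim over the whole region, including the part where one rate is poor and the other is excellent. There the good limb passes almost every time and gives no protection, so the error approaches the size of the poor limb alone. A rule that requires both limbs therefore holds 0.10 only if each limb holds 0.10 by itself. A figure obtained by multiplying the two tail probabilities with both rates at 65% covers only the part of the null where both rates are inadequate.

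This matters because feasibility is the primary objective (Section 2.1), this rule is its only formal test, and the synopsis (Section 1.1) makes the definitive trial conditional on PRISMS being feasible and beneficial. One good rate with one poor rate is exactly the case that a both-must-pass requirement is meant to catch. A reader of Section 7.2 would expect a wrong declaration there at most 1 time in 10.

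**Working it through.** **Inputs, all from Section 7.2.** Null boundary 65% and target 80% for each rate; at most 29 approached to recruit 20 dyads; at least 15 of 20 retained; stated power 76% and alpha 0.10. Independence of the two limbs is my assumption. It is not in the plan, but it reproduces both stated figures.

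**Formulas.** Needing no more than 29 approaches to recruit 20 is the same event as at least 20 successes in 29 trials.

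- Recruitment limb: R(p) = P(Bin(29, p) ≥ 20)
- Retention limb: Q(q) = P(Bin(20, q) ≥ 15)
- P(claim feasible) = R(p) × Q(q) under independence

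**Each limb alone.**

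| True rate | R | Q |
|---|---|---|
| 65% | 0.4076 | 0.2454 |
| 80% | 0.9507 | 0.8042 |

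**Reproducing the plan's figures.**

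- Power at p = q = 80%: 0.9507 × 0.8042 = 0.765, the stated 76%.
- Error at p = q = 65%: 0.4076 × 0.2454 = 0.100, the stated alpha.

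Of the neighbouring cut-offs tried (27 to 30 approached, 14 to 16 retained), only 29 and 15 give both figures. The stated alpha is therefore the value with both rates at 65%.

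**Error when only one rate is inadequate.** The last column gives limits that hold under any dependence: max(0, R + Q − 1) to min(R, Q).

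| p | q | P(claim feasible), independent | Any dependence |
|---|---|---|---|
| 65% | 80% | 0.4076 × 0.8042 = 0.328 | 0.212 to 0.408 |
| 80% | 65% | 0.9507 × 0.2454 = 0.233 | 0.196 to 0.245 |

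The largest error over the stated null is 0.408, at p = 65% with q near 100%. With q = 65% and p near 100% it is 0.245.

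**How fast the error falls below 65% (independence).**

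- Recruitment inadequate, q = 80%: 0.33 at p = 65%, 0.17 at 60%, 0.07 at 55%. It exceeds 0.10 for p from about 56.7% to 65%.
- Retention inadequate, p = 80%: 0.23 at q = 65%, 0.12 at 60%, 0.05 at 55%. It exceeds 0.10 for q from about 58.8% to 65%.

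**What a bare pass shows.** The exact one-sided 90% lower bound is 0.555 for 20 of 29 and 0.585 for 15 of 20. Neither excludes 65%.

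**Cost of true control at 0.10.** With 20 dyads, each limb must hold 0.10 alone. That needs at most 25 approached (error 0.083; 26 gives 0.142) and at least 17 of 20 retained (error 0.044; 16 gives 0.118). Power at 80% and 80% would fall to 0.6167 × 0.4114 = 0.25.

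**The case against.** The strongest reply is about weight. This is a pilot with 20 dyads, and Section 7.3 calls it exploratory rather than confirmatory. The primary objective also rests on satisfaction and perceived ease of use, for which Section 7.2 plans 95% confidence intervals. The error falls quickly once the inadequate rate is well below 65%, and the proposed change alters no threshold, sample size or decision. All of this stands, and it limits the practical effect. It does not make the stated alpha right: the exploratory remark in Section 7.3 waives multiplicity adjustment for comparisons and does not address the error rate of the feasibility test.

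A second reply is that the figures rest on independence. That is fair for the 0.10 itself: with both rates at 65%, the error under arbitrary dependence could lie anywhere from 0 to 0.245. It does not rescue the alpha statement, because with one rate at 65% and the other at 80% the error is at least 0.196 under any dependence.

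A third is that 80% for the good rate is a chosen value. It is the plan's own target, and the limit of 0.41 does not depend on it.

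Finally, correcting the sentence leaves a rule that does not control its stated null at 0.10. That is true. The reason to accept it is the cost shown above: real control with 20 dyads would cut power from 76% to about 25%.

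**Conclusion.** The concern holds. The 76% power is correct (0.765 under independence, 0.755 to 0.804 under any dependence). The 0.10 is correct only for the part of the null where both rates are 65% or lower, and only if recruitment and retention are independent. For the null as written, the false-claim probability is about 1 in 3 when recruitment alone is at 65% and about 1 in 4 when retention alone is, with the other rate at 80%. The maximum is 0.41, about four times the stated level. The calculation assumes that the limbs behave as binomial counts with constant rates and that approaches continue until 20 dyads are recruited, as the rule implies. Because the misstated figure describes the only formal decision rule for the primary objective, it must be corrected.

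**What to change.** Keep the thresholds and the sample size. Replace the alpha statement in Section 7.2 with wording such as:

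> Assuming that recruitment and retention are independent, the probability of wrongly claiming feasibility is at most 0.10 if both rates are 65% or lower. If only recruitment is inadequate, at 65%, it is 0.33 with retention at 80% and at most 0.41. If only retention is inadequate, at 65%, it is 0.23 with recruitment at 80% and at most 0.25. Power is 76% when both rates are 80%.

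Add that holding the full null at 0.10 with 20 dyads would reduce power to about 25%, as the reason for keeping the rule. In the report, give an exact one-sided lower confidence bound for each rate beside the decision, so that a bare pass is not read as evidence that both rates exceed 65%.

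Restating the null as both rates ≤ 65% would also make 0.10 valid, again under independence, but it fits poorly with the requirement in the same section that both rates be high.

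The cost is a few sentences in Section 7.2 and two bounds in the report. The stated error rate becomes less favourable; no patients are added, and data collection does not change.

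### The 0.58 width for the satisfaction interval needs all 10 PRISMS dyads to respond at T2; with 8 responding it is about 0.64, and the 0.29 per side is misleading

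*Combined protocol and SAP*

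**What the plan says.** Section 2.1 includes satisfaction with PRISMS and its perceived ease of use in the primary objective. Section 2.0 fixes the time of measurement: "At T2, we will collect quantitative data on participant satisfaction of and comfort with using PRISMS". No other collection time is given for it, and Section 4.3 puts the follow-up assessment about three months after baseline.

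Section 7.2 states the estimation aim: "we will estimate the proportion and associated 95% confidence interval of patients' satisfaction with and perceived ease use of PRISMS". It then gives the planning inputs, "With 10 couples in the PRISMS arm and expected satisfaction rate of 70" per cent, and the result, "the width of the 95% CI will be around 0.58 (0.29 for 1-side width". It does not name an interval method.

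The same paragraph tests retention against an alternative of at least 80% and calls the study feasible, on the retention side, if "more than 14 (≥ 15 out of 20) participants remained in the study". Section 7.3 commits to intention to treat, in which "all randomized participants will be analyzed according to their assigned group, regardless of the extent of intervention actually received". It gives no rule for a measure taken only at T2 when the T2 assessment is missing.

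**The concern.** The precision statement uses everyone randomised to the PRISMS arm as its denominator. The measure can come only from those still in the study at T2. Within one paragraph, the plan therefore allows for loss when it judges retention and allows for none when it states how precisely satisfaction will be estimated.

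A second issue is the single figure of 0.29 for one side. A reader will take it as plus or minus 0.29 around 0.70, that is, limits of 0.41 and 0.99. An exact interval at this sample size is clearly asymmetric, and its longer arm is on the low side, the side that matters when judging whether users were satisfied.

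What is at stake is the accuracy of the only stated precision for one component of the primary objective, and clarity about which dyads the reported proportion will describe.

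**Working it through.** **Inputs.** From Section 7.2: n = 10 PRISMS dyads, one response each; p = 0.70; 95% two-sided interval; retention of 80% at the boundary of the alternative; 15 of 20 as the lowest passing count. From Section 2.0: satisfaction is collected at T2.

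**Formulas.**
- Wald width = 2 × 1.96 × √(p(1 − p)/n).
- Exact (Clopper-Pearson), x satisfied of n: the lower limit is the 0.025 quantile of Beta(x, n − x + 1); the upper limit is the 0.975 quantile of Beta(x + 1, n − x).

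**Step 1: reproduce the plan's figure (n = 10, 7 satisfied).**
- Wald: 2 × 1.96 × √(0.21/10) = 0.568; half-width 0.284; limits 0.416 to 0.984.
- Exact: 0.348 to 0.933; width 0.586; half of that 0.293.

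The stated 0.58 lies between the two and within about 0.01 of each. Wilson (0.495), Agresti-Coull (0.504) and Jeffreys (0.513) do not match it.

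**Step 2: the per-side figure.** The exact interval for 7 of 10 extends 0.70 − 0.348 = 0.35 below the estimate and 0.933 − 0.70 = 0.23 above it. Neither is 0.29. The figure fits half of the exact width (0.293) slightly better than the Wald half-width (0.284), so it was probably obtained by halving an exact interval.

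**Step 3: respondents at T2.** At 80% retention with equal loss by arm, 0.80 × 10 = 8 PRISMS dyads respond. At 15 of 20 retained, an even split leaves 7 or 8 (7.5 on average). If each dyad were retained independently with probability 0.80 (an assumption made here), the chance that all 10 remain would be 0.8^10 = 0.11.

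**Step 4: width at 70% with fewer respondents.**

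| Respondents | Wald width | Exact width (interpolated where 0.70n is not whole) |
|---|---|---|
| 10 | 0.568 | 0.586 |
| 8 | 0.635 | 0.644 |
| 7.5 | 0.656 | 0.661 |
| 7 | 0.679 | 0.680 |

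With 8 respondents, 70% would be 5.6 dyads, which cannot occur. The two attainable exact results on either side of it are:
- 5 of 8: 0.245 to 0.915, width 0.670
- 6 of 8: 0.349 to 0.968, width 0.619

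The Wald interval at n = 8 has an upper limit of 0.70 + 0.318 = 1.018, above 1, which is a further reason to quote exact limits.

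**Step 5: denominator.** As an illustration only, 6 satisfied of 8 respondents is 75%. The same 6 of 10 randomised, with the two lost dyads counted as not satisfied, is 60%.

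**The case against.** The strongest reply is that nothing was miscalculated. The plan discloses its input of 10 couples, and 0.58 follows from it. That stands: a reader might infer an arithmetic error, and there is none. Nor does the total width depend on a symmetric interval, since the asymmetric exact interval also gives it; the symmetry problem is confined to the per-side figure. It would also go too far to say that the plan overstates the lower limit, because it states no limits at all.

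A second reply is that 80% is the boundary of an alternative hypothesis, not a forecast of dropout, and that no retention figure is given for the PRISMS arm. This also stands. Under the alternative, that arm could keep 9 or 10 dyads. The figure of 8 is a scenario drawn from the plan's own design value, so widths for both 8 and 10 should be shown.

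A reader might further infer that dropout biases the satisfaction proportion upward. The documents do not say why participants would leave or whether those who leave would be less satisfied. Upward bias is possible but not shown.

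Finally, the feasibility rule uses recruitment and retention only. Satisfaction has no threshold, and the trial is an exploratory pilot. All of that is true and limits the importance of the point. It does not remove the mismatch between a T2-only measure and a denominator with no loss.

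**Conclusion.** The point holds as a minor correction to a stated figure. The width of 0.58 requires complete T2 response in the PRISMS arm. With 8 of 10 responding it is about 0.64, an increase of about 0.06; the attainable exact widths are 0.62 and 0.67. This rests on retention at exactly 80%, equal loss by arm, 70% satisfied, and an interval method that reproduces the plan's own figure (Wald or Clopper-Pearson). A Wilson interval would be narrower (0.54 at 8 respondents, against 0.495 at 10), but it does not reproduce 0.58. The 0.29 per side is misleading, because the exact interval for 7 of 10 reaches 0.35 below and 0.23 above. The sample size and the feasibility rule are unaffected.

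**What to change.** In Section 7.2, replace the precision sentence with wording such as: *Using exact (Clopper-Pearson) limits, 7 of 10 satisfied gives a 95% CI of 0.35 to 0.93 (width 0.59); with about 8 of 10 dyads responding at T2, the width is about 0.62 to 0.67.* Delete the per-side figure of 0.29.

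In Section 7.3, state how PRISMS dyads without T2 satisfaction data are handled. As a sensitivity analysis, also report the proportion with those lost before T2 counted as not satisfied, since the proportion among completers may be biased upward.

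The cost is a few sentences and a slightly less favourable stated precision. No participants are added and no decision rule changes.
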